nomogram(<http://www.mskcc.org/applications/nomograms/prostate/PsaDoublingTime.aspx>). The post-treatment PSA doubling time will be calculated using the same nomogram from:

- (1) All PSA values obtained from the same clinical laboratory using the same PSA assay beginning with the PSA value at day 1 (week 0) and continuing until the end-of study (or month 24) value (PSADT₀₋₂₄).

(2) All PSA values obtained from the same clinical laboratory using the same PSA assay beginning with the PSA value at day 85 (month 3) to the day 253 (month 9) value (PSADT₃₋₉).

An increase in the PSA doubling time to at least double the baseline value, and at least 15 months, will be considered a PSA doubling time “response” [7].

D. Quantitative Total Bone Imaging (QTBI) using NaF PET/CT

An assessment of small volume bone metastatic disease (potentially not detected by standard bone scintigraphy) and tumor growth rates will be conducted using QTBI. Patients accrued to the Biomarker Cohort at designated clinical trial sites will be assessed at baseline, 3 months and 6 months by NaF PET/CT. Metastatic prostate cancer lesions in bone will first be localized and identified based on functional NaF PET uptake, assisted with the anatomical information provided by CT scans. Segmentation will be performed using an automatic segmentation method (e.g. a fixed SUV threshold), and adjusted with physician guidance. Scans from different time points will be registered to one another using an articulated registration technique employing a rigid registration of skeletal elements (bones) from CT followed by registration optimization by combining with deformable registration of bones and lesions from NaF PET/CT. The lesions between pre-treatment and follow-up scans will be matched to establish longitudinal correspondence of the lesions. For each patient, comprehensive treatment response metrics will be calculated, consisting of SUV_{total} (total disease burden), SUV_{max} (maximum intensity lesion), SUV_{mean} (average intensity), the number of lesions, and total volume of bone lesions. In addition, imaging response metrics will be calculated for each individual lesion. This methodology will specifically be used to assess the growth rate of bone metastatic disease by evaluating changes from baseline to month 3 and from month 3 to month 6. In terms of logistics, each of the clinical centers has the capacity and expertise to perform NaF PET imaging.

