Table: *Attainable power levels to detect differences in the 2-year MFS rates between study arms at the one-sided 5% significance level, assuming a sample size of 53 subjects per arm with an attrition rate of 15%*

	2-year MFS rate in DNA vaccine encoding PAP/rhGM-CSF arm				
2-year MFS rate in placebo/GM-CSF arm	0.66	0.68	0.70	0.72	0.74

0.38	0.87	0.91	0.94	0.96	0.97
0.40	0.82	0.87	0.91	0.94	0.96
0.42	0.77	0.82	0.87	0.91	0.94
0.44	0.70	0.77	0.82	0.87	0.91

Hence, if the true 2-year MFS rate in the Placebo/GM-CSF arm is 40% or less and the true 2-year MFS rate in the DNA vaccine encoding PAP/rhGM-CSF arm is greater than 70%, then the proposed sample size of 53 subjects per arm will provide at least 91% power to detect the difference in 2-year MFS rates between arms at the one-sided 5% significance level. Analogously, a difference of 40% versus 72% will be detected with 94% power while a difference of 40% versus 66% will provide 82% power.

Study Endpoints:

Primary endpoint: Metastasis-free survival (MFS)

Secondary endpoints:

1) Median PSA doubling time in patients with clinical stage D0 prostate cancer, in each study arm, prior to and after treatment. Pre-randomization serum PSA doubling time (PSA DT) is calculated from all available serum PSA values provided by the same clinical laboratory using the same assay three to six months prior to randomization. This value will be obtained using the Memorial Sloan-Kettering Cancer Center nomogram (<http://www.mskcc.org/mskcc/html/10088.cfm>). Post-randomization serum PSA doubling time will be calculated from day 1 to the 24 month follow up (end of study), and from month 3 to month 9 in the same fashion using:

- (1) All PSA values obtained from the same clinical laboratory using the same PSA assay beginning with the PSA value at day 1 (week 0) and continuing until the end-of study (or month 24) value (PSADT₀₋₂₄).
- (2) All PSA values obtained from the same clinical laboratory using the same PSA assay beginning with the PSA value at day 85 (month 3) to the day 253 (month 9) value (PSADT₃₋₉).

A two-fold increase or higher in the post-treatment (PSADT₀₋₂₄, PSADT₃₋₉) versus pre-treatment PSA doubling time and with a value greater than 15 months, will be considered a PSA doubling time “response” for an individual patient.

- 2) Safety and tolerability of the PAP-encoding DNA vaccine with GM-CSF as an adjuvant in patients with clinical stage D0 prostate cancer.

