- 3) Median progression-free survival, and PSA progression-free survival, in patients with clinical stage D0 prostate cancer, in each study arm. Progression is defined as the appearance of metastases by radiographic imaging using RECIST 1.1 criteria (appearance of a visceral lesion >

10 mm by CT or MRI, lymph node > 15 mm in short axis, or appearance of new lesions on bone scan consistent with metastatic disease), and median progression will be calculated from the date of randomization to the first evidence of metastatic disease. Progression will also be defined as the off-study date for those patients coming off-study prior to the 24-month time point to pursue other treatments, without evidence of metastasis. PSA progression is defined as a PSA value that is at least twice as large as its baseline (day 1) counterpart. PSA progression must be confirmed with a repeat PSA blood test at least two weeks later. The time to PSA progression will be defined as the interval between day 1 and the first time when a PSA value at least twice as large as the baseline value, also confirmed in the subsequent repeat PSA test, has been observed. All post-treatment PSA values have to be obtained from the same laboratory using the same assay. PSA progression-free survival times of subjects not experiencing PSA progression by the end of the follow-up period (24 months after the last patient has been randomized) will be censored. If lost-to-follow-up, the PSA progression-free survival time will be censored at the last available serum PSA measurement date. Similarly, if a patient experiences disease progression due to the appearance of metastases, PSA progression-free survival time will be censored at the date of the last available serum PSA measurement at the off-study time-point.

Laboratory endpoints:

An immune response will be defined as a PAP-specific T-cell frequency (by ELISPOT) or proliferation precursor frequency (by T-cell proliferation studies) at the completion of treatment that is at least 3-fold higher than the baseline T-cell frequency, and statistically different from media-only controls. An IgG immune response will be defined as a titratable PAP-specific IgG antibody response by ELISA, with titer of at least 1:100, detectable after immunization that was not detectable pre-immunization.

Biomarker endpoints:

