The 2-year MFS rates, as defined by RECIST 1.1 criteria, will be summarized in tabular format, stratified by study arm. The stratified Mantel-Haenszel test will be used to compare the 2-year MFS rates between arms. The stratification factors will include: Study cohort (initial vs. biomarker cohort), Gleason score (≤ 7 or > 7), PSA doubling time (< 3 months, 3-6 months, or 6-12 months), and baseline PSA at the time of screening (≤ 10 ng/mL or > 10 ng/mL). The survival function for metastasis-free survival will be estimated using the Kaplan-Meier method, and the comparison between the two arms will be made using a stratified logrank test at the one-sided 5% significance level. As available, meaningful quantiles of the metastasis-free survival time obtained based on Kaplan-Meier curves will be reported in each study arm. As an exploratory analysis of MFS, both univariate and multivariate Cox proportional hazards models will be used where study cohort (initial vs. biomarker cohort), Gleason score, baseline PSA doubling time and baseline PSA value will be included as covariates [62].

Secondary endpoints:

- 1) PSA DT response rates (based on both (PSADT₀₋₂₄ and PSADT₃₋₉) will be obtained for each study arm and will be summarized by standard descriptive statistics: means, standard deviations, medians and ranges. Fold changes in PSA DT from baseline to post-treatment (both (PSADT₀₋₁₄ and PSADT₃₋₉) will be calculated and the corresponding standard errors will be obtained by fitting a linear regression model (with log(PSA)). PSA doubling times in the two study arms will be compared using a weighted (by the inverse of the standard errors) Wilcoxon Rank Sum test and a 95% confidence interval for the difference will be constructed. A logistic regression model will be used to assess the treatment effect on PSA doubling time response rates, while adjusted for key prognostic factors that include Gleason score, baseline PSA doubling time and baseline PSA.

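### On its nearest reading, the inverse-SE weight in the PSA doubling-time test counts a patient less the more his doubling time lengthens, and it costs power

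*Combined protocol and SAP*

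**What the plan says.** Section 13, Statistical Analysis Plan, Secondary endpoints, item 1 takes two steps. First, "Fold changes in PSA DT from baseline to post-treatment" "will be calculated and the corresponding standard errors will be obtained by fitting a linear regression model (with log(PSA"). Second, "PSA doubling times in the two study arms will be compared using a weighted (by the inverse of the standard errors) Wilcoxon Rank Sum test", with a 95% confidence interval for the difference.

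The text does not give the scale of the SE (fold change, log fold change, doubling time or slope), the form of the weighted statistic, or whether residual variance is estimated per patient or pooled. The test sentence names doubling times as the quantity compared, but the only SEs introduced belong to fold changes.

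There are two post-treatment windows: day 1 to month 24 (PSADT0-24), and the one "beginning with the PSA value at day 85 (month 3) to the day 253 (month 9) value" (PSADT3-9). The sentence on SEs labels the first window 0-14, a label used nowhere else. Section 11.C takes doubling times from an external calculator: "The post-treatment PSA doubling time will be calculated using the same nomogram from" the listed values. It defines a response thus: "An increase in the PSA doubling time to at least double the baseline value, and at least 15 months, will be considered" a response.

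**The concern.** An inverse-SE weight is meant to favour precisely measured patients. The SE of a ratio, however, grows with the ratio. A fold change with a nearly flat post-treatment slope in its denominator has a large SE even when the PSA series is measured as well as anyone else's. The weight would then fall on the patients whose doubling time lengthens, which is the effect that the first secondary objective looks for. A doubling is also part of the protocol's own response definition. At stake is a false negative on that objective.

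**Working it through.** **Inputs from the document.** Shift 6.5 to 8.5 months, fold 8.5/6.5 = 1.31 (Section 4). 53 per arm, 28 + 25 by cohort (Section 13, Power Calculation). Two-sided 5% (end of Section 13). At least four pre-treatment values over 12 weeks to 6 months, doubling time under 12 months (Section 7.A). Scheduled values in months 3–9: Days 85, 169 and 253, plus Day 127 in the biomarker cohort (Section 10). The plan gives no power for this test, so there is no figure to reproduce.

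**Assumed.** Common noise SD of log PSA 0.10 or 0.20; lognormal baseline doubling time with median 6.5 months and log-SD 0.5 or 0.3; five pre-treatment values over 5.5 months; complete series.

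**Step 1: the weight.** Let b be the slope of log PSA and s its SE. Fold change FC = b_pre/b_post, and by the delta method

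SE(FC) = (FC/b_pre) × √(s_pre² + FC² s_post²).

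With the same baseline slope, schedule and noise, the weight relative to an unchanged patient is

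1 / {FC × √[(s_pre² + FC² s_post²)/(s_pre² + s_post²)]},

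which is at most 1/FC for FC ≥ 1. Since s² = σ²/Sxx, the noise SD σ cancels.

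Example, first cohort, months 3–9: post-treatment Sxx = 2 × 84² = 14,112; pre-treatment Sxx ≈ 17,500. At FC = 2 the bracket is (1/17,500 + 4/14,112)/(1/17,500 + 1/14,112) = 2.66, its root 1.63, and the weight 1/(2 × 1.63) = 0.31. At FC = 4 the bracket is 9.3 and the weight 1/(4 × 3.05) = 0.08.

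For pre-treatment layouts from 4 values over 12 weeks to 7 over 6 months:

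| Doubling time | Months 3–9 | Months 0–24 |
|---|---|---|
| ×2 | 0.29–0.39 | 0.47–0.50 |
| ×4 | 0.08–0.12 | 0.19–0.24 |

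This holds while PSA rises. SE(FC) depends on the size of b_post, so the weight nears zero for a flat PSA and recovers for a clearly falling one. Pooling the residual variance does not change it.

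**Step 2: power.** Slopes are ranked throughout, so differences isolate the weights. The statistic is the sum of w_i w_j sign(x_i − x_j) over vaccine–control pairs, divided by the sum of w_i w_j; 399 permutations within cohort; 1,000 trials per cell (Monte Carlo SE at most 1.6 points). Power in % at baseline log-SD 0.5, noise SD 0.10 / 0.20:

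| Weight | Months 3–9 | Months 0–24 |
|---|---|---|
| None | 74 / 55 | 89 / 88 |
| 1/SE(FC), pooled variance | 53 / 36 | 67 / 68 |
| 1/SE(FC), separate variances | 47 / 33 | 58 / 60 |
| 1/SE(post-treatment slope), separate | 30 / 18 | 86 / 84 |
| 1/SE(post-treatment slope), pooled | 74 / 55 | 89 / 88 |

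Pooled 1/SE(FC) loses 21 / 19 and 22 / 20 points; repeat runs put the range at about 17–22. A different weighted statistic, the difference in weighted mean ranks, loses less: 62 / 41 in months 3–9 (12 / 14 points) and 75 / 75 in months 0–24 (14 / 13 points). Null rejection was 4–6% throughout.

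**Step 3: baseline spread.** The weight also contains b_pre, so slow risers are discounted even when unchanged, and the loss depends on how much baseline doubling times vary. At log-SD 0.3, pooled 1/SE(FC) loses about 8–19 points in months 3–9 and 1–2 in months 0–24 (for example 99.8% to 98.0%, near the ceiling).

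**Step 4: separate slope SEs in months 3–9.** A straight-line fit uses two parameters, which leaves 3 − 2 = 1 residual degree of freedom in the first cohort and 4 − 2 = 2 in the biomarker cohort. Such SEs mostly reflect chance fit; the median effective sample size was 16 of 106. A further rule, "PSA progression must be confirmed with a repeat PSA blood test at least two weeks later", adds a value for some patients only.

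**The case against.** **The log scale is as natural.** The SEs come from a regression on log PSA, so the SE of the log fold change may be meant. It multiplies each weight by FC: in the layout worked above, a doubling in months 3–9 rises from 0.31 to about 0.6, and in months 0–24 the weight is close to 1. That answers the discount on lengthening. It does not recover the power: the loss is still about 20 points in both windows at log-SD 0.5 and noise 0.10, because slowly rising PSA remains down-weighted.

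**Weighting can be useful.** A reader might infer that no weighting improves on an unweighted test. The documents do not support that. Patients leave study at metastasis (Section 8.B), control two-year metastasis-free survival is assumed to be 40% (Section 13), and PSADT0-24 stops at the end-of-study value, so series will differ in length. With noise SD 0.30, baseline log-SD 0.3, 45 per arm and exits matching 40% and 70% two-year metastasis-free survival, pooled slope-SE weights gave 93% power against 89% unweighted. In a more extreme setting (very unequal noise, little spread in true slopes, half the patients gone by month 9) they gave 92% against 70%. In ordinary settings they tie. The natural-scale fold-change weight beat the unweighted test in no setting run.

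**The size rests on assumptions.** This stands. Noise, baseline spread and the statistic are not in the documents; the direction is firm, the 20 points are not. The unweighted figures are also stratified by cohort only, not by the 2 × 3 × 2 = 12 randomisation cells.

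**Non-rising PSA.** A reader might infer that the response rule counts a flat or falling PSA as a failure. The doubling time comes from an external nomogram whose handling of that case is not shown, so this cannot be concluded.

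**Conclusion.** The point holds in limited form. The plan leaves the SE and the statistic undefined. On the reading its sentences most directly support, the weight discounts the patients in whom the vaccine appears to work. That discount is algebra: it holds at any common noise level while PSA is rising. The loss of power is conditional: about 20 points in both windows at an assumed baseline log-SD of 0.5, and about 8–19 (months 3–9) and 1–2 (months 0–24) at 0.3. All of these assume the shift in Section 4, 53 per arm, complete series, noise SD 0.10–0.20, pooled variance and the product-weighted statistic.

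It would be wrong to read this as a threat to validity or to the main result. Type I error is preserved, and the primary metastasis-free survival analysis and PSA progression-free survival do not use these weights. The change is worth making because it is cheap and the objective is the first secondary one.

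**What to change.** 1. Do not weight by the SE of the fold change.
2. Make the main comparison an unweighted Wilcoxon test, stratified by cohort or by the randomisation factors, on the post-treatment slope of log PSA. A non-rising PSA then ranks as most favourable without a special rule. With 106 patients the 12 randomisation cells will be thin, so say in advance whether any are combined.
3. Give the 95% interval as a Hodges–Lehmann difference in slopes.
4. If weighting is kept, make it a sensitivity analysis: slope SE, pooled residual variance, and a written definition of the statistic.
5. Reconcile the 0-14 label with PSADT0-24, and state how the nomogram result is handled when PSA does not rise.

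The cost is SAP wording; the data are the same. The downside is that the unweighted test may be somewhat less efficient if PSA precision differs greatly between patients, which the sensitivity analysis would show.

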For each of the immunizations/treatments: 0.6 mL of 0.2 mg/mL pTVG-HP (or 0.6 mL phosphate-buffered saline (PBS) from placebo vial) will be withdrawn and used to reconstitute 250 µg GM-CSF. 0.25 mL will then be drawn into each of two tuberculin syringes. This effectively provides a 100-µg dose of DNA and 208 µg GM-CSF.

The vaccine/GM-CSF (or PBS/GM-CSF) will then be administered intradermally on the deltoid area of the lateral aspect of the arm (left arm, preferentially) in two adjacent sites, with the total syringe contents (0.25 mL) administered at each site.

7. Patient Selection

A. Inclusion Criteria

1. Patients must be at least 18 years of age with a histologic diagnosis of adenocarcinoma of the prostate
2. Patients must have completed local therapy by surgery and/or ablative radiation therapy at least 3 months prior to entry, with removal or ablation of all visible disease, including seminal vesical and/or local lymph node involvement.
3. Patients must have high-risk clinical stage D0 disease defined by the following:
 - In patients previously treated by prostatectomy, must have evidence of rising PSA with measurements at least two weeks apart, and final serum PSA value must be ≥ 2 ng/mL.
 - In patients previously treated with ablative radiation therapy, an absolute increase in serum PSA by at least 2 ng/mL over nadir PSA value after radiation therapy.
 - All patients must have at least four serum PSA values determined over a 12-week-to-six-month period of time prior to study entry from the same clinical laboratory. All available PSA values during this period (up to 6 months) will be used to calculate a PSA doubling time, according to the Memorial Sloan-Kettering Cancer Center nomogram
 - (<http://www.mskcc.org/applications/nomograms/prostate/PsaDoublingTime.aspx>).
 - The PSA doubling time calculated from this nomogram, up to and including the value obtained at screening, must be < 12 months
4. Patients with a prior history of a second malignancy are eligible provided they have been treated with curative intent and have been free of disease greater than three years. There will be no exclusion for patients with a history of basal cell carcinoma, squamous cell skin cancer, or *in situ* carcinoma that has been adequately treated.
5. Patients who are sexually active must use a reliable form of contraception while on study and for 4 weeks after the last immunization.
6. ECOG performance score < 2 and life expectancy of at least 4 months.

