This will be a randomized, double-blinded, multi-institutional phase II trial designed to evaluate the effect of serial intradermal vaccinations of a DNA vaccine encoding PAP with rhGM-CSF on time to disease progression as compared to rhGM-CSF alone. 56 patients are to be accrued as part of a DOD sponsored trial. An additional 50 patients (BIOMARKER COHORT), funded by a separate sponsor, will be accrued using the same treatment protocol (same study population, treatment schedule, inclusion/exclusion criteria etc.) Additional biomarker endpoints will be measured in the BIOMARKER COHORT. The treatment, assessment and analysis of these 50 patients and associated data are NOT part of the DOD sponsored trial. There will be no interim analysis conducted after the initial 56 patients have been accrued and the study will remain blinded until the completion of the proposed total number of 106 patients has been completed and all patients have been followed for the primary efficacy endpoint assessment. Study arms will be defined as follows:

Arm 1: pTVG-HP (100 µg) with rhGM-CSF (208 µg) administered intradermally (i.d.) biweekly for 6 total doses, then every 3 months to complete a 2-year treatment period

Arm 2: rhGM-CSF (208 µg) administered intradermally (i.d.) biweekly for 6 total doses, then every 3 months to complete a 2-year treatment period

A. Study Arm Assignment and Toxicity Assessment

Patients with non-metastatic prostate cancer, with evidence of rising PSA, and a calculable PSA doubling time with at least 4 serum PSA values collected over a 3-6 month period of time, will be invited to participate. Subjects will be randomly assigned to a treatment group, stratified by original Gleason score (≤ 7 or > 7), PSA doubling time (< 3 months, 3-6 months, or 6-12 months), and baseline PSA at the time of screening (≤ 10 ng/mL or > 10 ng/mL). Given the absence of significant adverse events observed in a previous phase I study, no adverse events $>$ grade 2 are anticipated. However, all study patients will be evaluated for evidence of toxicity, and further accrual to either treatment arm will be discontinued if the toxicity rate is deemed to be excessive. A toxicity rate of 20% for Grade 3 events (or Grade > 1 autoimmune events) or

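### The continuous between-arm test of PSA doubling time names neither the quantity ranked nor any baseline adjustment, which can cost power on a secondary endpoint

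*Combined protocol and SAP*

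**What the plan says.** Section 13, Statistical Analysis Plan, Secondary endpoints, item 1, contains three relevant steps.

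- It calculates "Fold changes in PSA DT from baseline to post-treatment" and adds that "the corresponding standard errors will be obtained by fitting a linear regression model (with log(PSA" as the response.
- It then gives the continuous between-arm test: "PSA doubling times in the two study arms will be compared using a weighted (by the inverse of the standard errors) Wilcoxon Rank Sum test", with a 95% confidence interval for the difference. No covariate or stratum is attached to this test.
- It ends with a logistic model for the dichotomised doubling time response, "adjusted for key prognostic factors that include Gleason score, baseline PSA doubling time and baseline PSA".

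Under Study Endpoints in the same section, the endpoint is "Median PSA doubling time in patients with clinical stage D0 prostate cancer, in each study arm, prior to and after treatment". Two post-treatment windows are used, months 0 to 24 and months 3 to 9.

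Every man needs a baseline doubling time to be eligible (Section 7.A, item 3), and randomisation is stratified on it in three levels: "PSA doubling time (< 3 months, 3-6 months, or 6-12 months" (Section 8.A). The stratified tests of metastasis-free survival and the stratified Cox models for progression-free and PSA progression-free survival use this factor.

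**The concern.** The continuous comparison is the most informative test of secondary objective 1, yet it is the one doubling time comparison between arms that names no baseline adjustment. The inverse standard errors weight for precision; they do not adjust for baseline. If a man's PSA growth before treatment predicts his growth afterwards, leaving that information out widens the comparison, and a real slowing of PSA growth is more likely to be missed.

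The ranked quantity is also not fixed. Post-treatment doubling times and fold changes have different variances and different power, and the choice should not remain open until the data are seen.

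**Working it through.** **1. Working sample size, checked against the plan's own figure.** 53 per arm less 15% attrition is 53 × 0.85 = 45.05, so 45 per arm. For 40% versus 70% at one-sided 5%, with unpooled variance: Φ(0.30/√((0.24 + 0.21)/45) − 1.645) = Φ(3.000 − 1.645) = 0.912. The plan states 91% (a pooled variance gives 0.899). The documents give no power, effect size or SD for the doubling time test.

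**2. Reference effect.** On the log scale, at two-sided 5% and with rank-test efficiency 3/π, 80% power for ranking post-treatment values needs (1.960 + 0.842) × √(2/(45 × 3/π)) = 2.802 × 0.2157 = 0.604 SD.

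**3. Power by analysis.** Power = Φ(2.802/k − 1.960). Here k = 1 for post-treatment values, √(2(1 − ρ)) for fold change and √(1 − ρ²) for a baseline-adjusted analysis. ρ is the correlation of log doubling time before and after treatment. It is an assumption, and equal variances before and after are assumed too.

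| ρ | Post values | Fold change | Adjusted | Gain over post | Gain over fold |
|---|---|---|---|---|---|
| 0 | 80.0% | 50.8% | 80.0% | 0 | 29.2 |
| 0.2 | 80.0% | 60.1% | 81.6% | 1.6 | 21.5 |
| 0.3 | 80.0% | 65.8% | 83.6% | 3.6 | 17.8 |
| 0.5 | 80.0% | 80.0% | 89.9% | 9.9 | 9.9 |
| 0.7 | 80.0% | 95.1% | 97.5% | 17.5 | 2.4 |

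The adjusted analysis needs (1 − ρ²) of the post-value sample: 0.91, 0.75 and 0.51 at ρ = 0.3, 0.5 and 0.7. Relative to fold change it needs (1 − ρ²)/(2(1 − ρ)) = (1 + ρ)/2: 0.65, 0.75 and 0.85.

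**4. Scale from the documents.** Section 4 reports an uncontrolled change in median doubling time from 6.5 to 8.5 months. The log ratio is ln(8.5/6.5) = 0.268. In slope terms, 6.5/8.5 = 0.765, about 24% slower growth. With an assumed SD of log doubling time of 0.4, 0.6 or 0.8 and ρ = 0.5, power is 87.5%, 54.5% or 34.3% for either rank test, and 94.8%, 66.8% or 43.4% adjusted.

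**5. Simulation with randomisation stratified on baseline** (45 per arm on average, three strata, unweighted, effect 0.604 SD). At ρ = 0.3, 0.5 and 0.7:

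- Rank test on post values: 79.7%, 81.5%, 83.8%.
- Rank ANCOVA: 82.8%, 89.1%, 96.8%.
- Type I error of the post-value test: 4.4%, 3.4%, 1.3%. Stratifying randomisation and then ignoring the factor makes this test conservative.

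**6. Simulation of PSA series** (45 per arm, 25% slower growth, departures at the planned 40% and 70% metastasis-free rates, assumed variances).

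- Months 3 to 9: adjusted 0.53-0.96, rank test on post values 0.44-0.67. Against fold change the difference ran from −3 to +10 points.
- Months 0 to 24: SE-weighted adjusted 0.56-0.98, SE-weighted rank test on post values 0.46-0.65. Against fold change, unweighted ANCOVA was no better and SE-weighted ANCOVA was mixed, −8 to +8 points.
- Type I error of the adjusted test was 0.03-0.06.

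A further run for months 0 to 24 used 48 per arm, the same slowing and four noise settings, with simulation error of about 2 points. The SE-weighted rank test on fold change gave 1.00, 0.82, 0.87 and 0.69. Unweighted slope ANCOVA gave 0.99, 0.78, 0.83 and 0.65. SE-weighted ANCOVA gave 1.00, 0.79, 0.95 and 0.76. The weights matter because men who leave early have short PSA series.

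**The case against.** The strongest reply is that the plan may already use baseline. The sentence before the test calculates fold changes, the standard errors that serve as weights are introduced there, and the endpoint is defined before and after treatment. On that reading each man's baseline is inside the outcome. The same paragraph also gives a logistic analysis adjusted for baseline doubling time. A reader might infer that the plan ignores baseline doubling time altogether, and the text does not support that. What survives is that the ranked quantity is not named, and that fold change carries the full noise of a baseline estimated from as few as four PSA values.

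The size of the loss is also uncertain. It depends on ρ, which is not given. Eligibility restricts the baseline range ("The PSA doubling time calculated from this nomogram, up to and including the value obtained at screening, must be < 12 months"), which may lower ρ. A reader might take baseline doubling time to be the strongest predictor of later doubling time. The Introduction links doubling time to metastasis and death, not to later doubling time. This objection stands as a limit on the magnitude. A low ρ shrinks the gain over post values but enlarges the gain over fold change.

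The formulas in steps 2 to 4 and the simulation in step 5 omit the inverse-SE weights and early departures. Step 6 includes them, and there the advantage over fold change for months 0 to 24 is not consistent. That stands.

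Finally, a rank test is insensitive to the extreme doubling times that arise when PSA flattens, so it is not without merit. That stands, and it is a reason to keep the test as a sensitivity analysis.

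**Conclusion.** The point holds as a matter of efficiency and wording. The continuous test has no covariate or stratum adjustment although the baseline measure is available for every man and stratifies randomisation, and its outcome is not clearly named.

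Read literally, the test ranks post-treatment values. The loss then rises with ρ: about 4, 10 and 17.5 points from an 80% base at ρ = 0.3, 0.5 and 0.7. Read as fold change, the loss is about 18, 10 and 2 points by formula, and simulation of months 0 to 24 shows no consistent loss. These figures rest on an assumed ρ and assumed variances.

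A reader might infer bias or an inflated error rate. Neither follows: randomisation protects the comparison, and the unadjusted test is if anything conservative. The endpoint is secondary and no power is claimed for it, so this is a free improvement of optional to modest priority.

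**What to change.** Before unblinding, amend Secondary endpoints, item 1, to do four things.

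1. Name the compared quantity for each window (months 0 to 24 and months 3 to 9).
2. Make the between-arm test baseline-adjusted while keeping the precision weights. One choice is an inverse-SE-weighted ANCOVA of the post-treatment log-PSA slope on arm, with pre-treatment log-PSA slope, Gleason score and baseline PSA as covariates. A rank ANCOVA is an alternative.
3. Report the effect as a slope difference with its 95% confidence interval, plus model-predicted doubling times per arm at a stated baseline. Doubling time is ln 2 divided by the slope, so an additive slope difference has no single back-transformation.
4. Keep the weighted Wilcoxon test as a sensitivity analysis that is robust to extreme doubling times.

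If the team prefers to stay with a stratified rank test, a van Elteren test over the three baseline strata recovers part of the gain. In simulation with simple 1:1 allocation and no weights it gave 81.1%, 84.5% and 93.6% at ρ = 0.3, 0.5 and 0.7, against about 79% unadjusted.

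The cost is SAP wording. The log-PSA regressions are already planned and no new data are needed.
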